13.12. PK Analysis

Individual plasma levels of eteplirsen will be listed with the corresponding time related to IP administration and summary statistics will be generated by per-protocol time of collection.

PK analysis of plasma concentration-time data of eteplirsen will be performed using nonlinear mixed-effects modeling. For population PK analyses, data from this study may be combined with those of other studies to support a relevant structural model. Available patient characteristics (demographics, laboratory variables, genotypes, concomitant medications, etc.) will be tested as potential covariates affecting PK parameters. A separate population PK analysis plan will outline the methodology that will be utilized in developing an exposure-response model that would take into account the disease natural progression and the available eteplirsen concentration data to relate its exposure with the change in disease progression.

13.13. Interim Analyses

An interim analysis will be performed after approximately 35 patients with baseline 6MWT between 300 and 450 meters, inclusive, have completed their Week 96 assessments. Given the small size of the untreated control group, external control patients, including those amenable to exon 51 skipping, may be identified and compared to the eteplirsen-treated group. The details of the interim analysis will be specified in a SAP before the database lock for the interim analysis.

13.14. Other Statistical Issues

Additional analyses may be conducted. Any such analyses will be detailed in the SAP.

14. SPECIAL REQUIREMENTS AND PROCEDURES

14.1. Compliance with Ethical and Regulatory Guidelines

This study will comply with the requirements that are enunciated in the European Clinical Trial Directive 2001/20/EC and in the US CFR.

14.2. Institutional and Ethics Review

This study will be conducted in full compliance with the IRB regulations in 21 CFR 56 and/or the European Clinical Trial Directive 2001/20/EC. Before enrollment of patients into the study, the protocol and informed assent (for patients, if applicable) and informed consent (for parents/legal guardians) documents will be reviewed and approved by the appropriate IRB/IEC and regulatory authority. Amendments to the protocol will be subjected to the same IRB/IEC and regulatory authority review requirements as the original protocol. The Investigator will promptly notify the IRB/IEC and Sponsor of any SAEs or of any other information that might affect the safe use of the IP during the study. IRB approvals/IEC positive opinions and regulatory authorities' approvals must be sent to the Sponsor, or its designee, before initiation of the study or before an amendment is instituted. All correspondence with the IRB/IEC and the regulatory authority should be retained in the study regulatory files.

14.3. Informed Consent/Assent and Authorization for Use and Disclosure of Protected Health Information

Written informed consent from each patient's parent(s) or legal guardian(s) and written assent from each patient, if applicable, must be obtained at the Local Site, Hub Site, and Surgical Unit (if applicable) before any study-specific screening or Baseline period evaluations are performed at these respective study sites. In addition, each patient's parent/guardian must sign a Study Consent form (Treated or Untreated Control) at their Local Site Day 1 visit, prior to any Day 1 study procedures being performed. In addition, if the patient's local site is different from their Hub Site, the patient's parent/guardian must re-consent at their Hub Site with the appropriate Study Consent form at their Week 12 Functional Assessment visit, prior to any Week 12 study procedures being performed. For patients enrolled prior to implementation of Amendment 2 of the protocol, the patient's parent/guardian must re-consent (at both the local site, and Hub Site if different from the local site) as soon as possible after implementation of Amendment 2 for the patient to continue in the study beyond Week 48. Patients enrolled prior to implementation of protocol Amendment 2 must re-consent at the surgical unit if they are scheduled for biopsy at Week 72 or Week 96. For each of these consent processes, written assent from each patient, if applicable, must also be obtained in addition to the written informed consent by the parent/guardian. One copy of the signed informed consent/assent documents will be given to the patient: the Investigator will retain the original copies of these documents.

The informed consent/assent documents, as prepared by the Sponsor or designee, must be reviewed and approved by the IRB/IEC and regulatory authorities, as applicable, before initiation of the study. The informed consent document must contain the basic required elements of

consent and additional elements, as applicable, as specified in the 21 CFR 50.25 and the European Clinical Trial Directive 2001/20/EC.

14.4. Compliance with the Protocol

All processes and procedures defined in this protocol will be adhered to. Emergency departures from the protocol that eliminate an apparent immediate hazard to a particular patient and that are deemed by the Investigator as crucial for the safety and wellbeing of that patient may be instituted for that patient only and documented as deviations. The Investigator will contact the medical monitor as soon as possible regarding such a deviation. These departures do not require preapproval by the IRB/IEC; however, the IRB/IEC and Medical Monitor must be notified in writing as soon as possible in accordance with the IRB/IEC policies after the departure has been made.

14.5. Confidentiality

14.5.1. Data

All information regarding the nature of the proposed investigation that is provided to the Investigator by the Sponsor, the Sponsor's designee, or the study monitor, with the exception of information that is required by law or regulations to be disclosed to the IRB/IEC, the patient's parent(s) or legal guardian(s) or the appropriate regulatory authority, must be kept in confidence by the Investigator in accordance with current Health Insurance Portability and Accountability Act (HIPAA) standards and/or European standards.

14.5.2. Patient Anonymity

The anonymity of participating patients will be maintained to the extent required by applicable laws and in accordance with current HIPAA standards. Patients will be identified by their initials and an assigned patient identification number on the CRFs and other data collected by the Sponsor. The Investigator must maintain all documents related to the study that identify the patient (e.g., the signed informed consent document) in strict confidence, except to the extent necessary to allow auditing by the appropriate regulatory authorities, the IRB/IEC, the study monitor, or the Sponsor or its representatives.

15. STUDY DOCUMENTATION AND GENERAL INFORMATION

15.1. Essential Study Documents

The following documentation will be collected prior to study enrollment:

- Signed Form FDA 1572, or equivalent
- Curriculum vitae for each person on the Form FDA 1572 or equivalent
- Signed Financial Disclosure Forms for each person listed on the Form FDA 1572 or equivalent
- IRB/IEC approval for all study materials (ICF, Protocol, any recruitment materials, etc.) and IRB/IEC membership list
- Clinical laboratory normal ranges, when appropriate
- Clinical laboratory licenses (CAP/CLIA or other)
- Signed final protocol page
- IB acknowledgement
- A blank copy of the IRB-/IEC-approved informed consent (and assent documents, if applicable) and authorization
- A fully executed Clinical Trial Agreement and Confidentiality Agreement

These documents are among the critical documents required before study enrollment is to occur. Copies of these documents, as well as supplemental information, such as the Investigator's Brochure, Pharmacy Manual, CRF Completion Guidelines, final protocol, as specified in the Clinical Operations Manual and/or Regulatory Binder, must be kept on-site in a designated study site file.

The study site files will also contain, patient accountability records, drug accountability (receipt/dispensing) records, Sponsor/Investigator correspondence, IRB/IEC correspondence, deviations, biological sample records, and SAE and IND safety reports / Safety Alert Letters.

15.2. General Information

The Investigator should refer to the current Investigator's Brochure along with subsequent Safety Alert Letters, the Clinical Study Operations Manual, Pharmacy Manual, Laboratory Manual, CRF Completion Guidelines, and all other study-specific information that is provided during the study initiation visit or by the study monitor.

15.3. Dissemination of Study Results

The information that is developed during the conduct of this clinical study is considered to be strictly confidential. This information may be disclosed only as deemed necessary by Sarepta Therapeutics Inc. However, at the conclusion of this clinical study, a clinical study report will be

prepared. In addition, a manuscript will be prepared for publication in a reputable scientific journal under the direction of the Sponsor. Sarepta Therapeutics Inc., will publish and communicate the clinical study results, irrespective of positive or negative findings. Data generated for this study will be exclusively owned by Sarepta Therapeutics Inc., as detailed in the Clinical Trial Agreement. The study will be registered on ClinicalTrials.gov. After completion of the study, results will be disseminated through ClinicalTrials.gov.

15.4. Product Handling and Complaints Reporting

If there are any issues during the course of the study related to the quality of the IP, the Investigator, clinical site pharmacist or pharmacy designee should contact the Sponsor or designated clinical research organization.

1. INTRODUCTION

The purpose of this statistical analysis plan (SAP) is to provide a detailed description of the statistical methods for the final analysis of the Sarepta Therapeutics Study 4658-301, titled “An Open-Label, Multicenter, Study with a Concurrent Untreated Control Arm to Evaluate the Efficacy and Safety of Eteplirsen in Duchenne Muscular Dystrophy.”

This SAP is based on protocol version 5 (Amendment 4), dated 02 Jun 2017.

2. STUDY OBJECTIVES

The primary objective of this study is to evaluate the effect of eteplirsen on ambulation, endurance, and muscle function as measured by change from Baseline to 96 weeks in the 6-minute walk test (6MWT) as compared to an untreated control arm of Duchenne muscular dystrophy (DMD) patients amenable to exon skipping.

The secondary objectives are to evaluate:

- The effect of eteplirsen on dystrophin expression as measured by the change from baseline in dystrophin quantification by Western blot and dystrophin intensity levels determined by immunofluorescence in biopsied muscle tissue
- The effect of eteplirsen on respiratory muscle strength as measured by the difference in change from Baseline in forced vital capacity (FVC) % predicted
CC1
[REDACTED] between the eteplirsen-treated and the untreated control arm of DMD patients amenable to exon skipping
- The safety and tolerability of eteplirsen

The additional objective is to evaluate the clinical and pharmacodynamic effects of eteplirsen treatment for up to 96 weeks.

The pharmacokinetic (PK) objective is to evaluate the PK properties of eteplirsen via a population PK model.

3. STUDY ENDPOINTS AND OTHER VARIABLES

[figure not shown]
3.1. Efficacy Endpoints

The primary efficacy endpoint is the change from Baseline to Week 96 in 6MWT.

The secondary efficacy endpoints are:

- Change from Baseline in dystrophin protein levels quantified by Western blot in eteplirsen-treated patients
- Change from Baseline in dystrophin intensity levels determined by immunofluorescence in eteplirsen-treated patients
- Ability to rise independently from the floor (without external support)
- Loss of ambulation (LOA)
- Change from Baseline in FVC % predicted
- Change from Baseline in North Star Ambulatory Assessment (NSAA) total score

CCI

[figure not shown]
3.2. Safety Endpoints

The following safety endpoints will be summarized:

- Incidence, type, frequency, severity, and relationship to study drug of treatment-emergent adverse events (TEAE), serious adverse events (SAE), adverse events of special interest (AESIs), and adverse events (AEs) leading to discontinuation
- Concomitant medications and physiotherapeutic interventions

- Incidence of clinical laboratory abnormalities including chemistry, hematology, coagulation, and urinalysis
- Incidence of abnormalities in vital signs and physical examinations
- Incidence of abnormalities on electrocardiogram (ECG) and echocardiogram (ECHO): ejection fraction and fractional shortening

CCI

3.4. Pharmacokinetic Endpoints (Eteplirsen-treated Patients Only)

PK concentrations of eteplirsen will be listed and summarized. PK parameters for eteplirsen will be estimated based on sparse sampling. The effects of demographic characteristics, concomitant medications, laboratory values, and other covariates on eteplirsen PK will be evaluated.

4. STUDY OVERVIEW

4.1. Study Design

This is an open-label, multicenter study to evaluate the efficacy and safety of eteplirsen in patients with genotypically confirmed DMD with exon deletions amenable to exon 51 skipping (eteplirsen-treated group), as compared with an untreated control arm of DMD patients amenable to exon skipping (untreated control group). Note that patients in the untreated control arm are not amenable to exon 51 skipping.

Patients will be evaluated for inclusion during a Screening/Baseline period of up to 10 weeks (not including time needed for genotyping if the patient has not been previously genotyped). Eligible patients for the eteplirsen-treated group will receive once weekly intravenous infusions of 30 mg/kg eteplirsen for 96 weeks, followed by a safety extension (not to exceed 48 weeks), until the product is commercially available or until patients can transition into a separate eteplirsen study. Eligible patients in the untreated control group will not receive treatment with eteplirsen but will complete selected study assessments through 96 weeks.

An overview of the study design through Week 96 is presented in Figure 1.

[figure not shown]

Figure 1 Overview of Study Design through Week 96

4.2. Sample Size and Power

This study will enroll approximately 90 patients with a Baseline 6MWT distance of 300 to 450 meters, including approximately 70 patients in the eteplirsen-treated group and approximately 20 patients in the untreated control group. CCI

CCI

Additionally, approximately 20 patients (10 eteplirsen-treated vs 10 untreated control) with a Baseline 6MWT distance of >450 meters will be enrolled.

4.3. Randomization and Blinding

There will be no randomization for the assignment of patients to the 2 treatment groups (eteplirsen-treated vs untreated control). Patients who are amenable to exon 51 skipping will be assigned to the eteplirsen-treated group and receive weekly infusions of eteplirsen 30 mg/kg; and patients who are not amenable to exon 51 skipping will be assigned to the untreated control group.

Upon qualification for the study during the Baseline visit, patients in the eteplirsen-treated group will undergo a muscle biopsy and will be randomized in a 1:2:1:1 ratio to undergo a second muscle biopsy at Week 24, 48, 72, or 96. Patients in the untreated control group will not undergo muscle biopsy at any time during the course of the study.

4.4. Planned Analyses

4.4.1 Interim Analysis

An interim analysis was performed after approximately 35 patients with a Baseline 6MWT between 300 and 450 meters, inclusive, had completed their Week 96 study assessments.

This interim analysis was detailed in a separate SAP which was finalized on 28 Jun 2017.

4.4.2 Final Analysis

A final analysis of safety and efficacy will be conducted once the last patient completes the entire study and the resulting database is cleaned, quality assured, locked, and unblinded. All statistical analyses will be performed by or under the supervision of the Sponsor. All available data will be included in data listings and tabulations. Due to the small population size and large dropout rate of the untreated control group, only descriptive summaries will be presented. An external control dataset will be identified and used to evaluate the effect of eteplirsen treatment. The statistical methods for the identification and use of the external control dataset will be presented in a supplemental SAP.

5. ANALYSIS SETS

The following analysis sets will be defined.

5.1. Efficacy Set

The efficacy set will consist of all patients in the eteplirsen-treated and untreated control groups who have at least 1 post-baseline functional assessment.

5.2. Primary Efficacy Set

The primary efficacy set will consist of all patients in the efficacy set who have a Baseline 6MWT distance of 300 to 450 meters, inclusive.

5.3. Safety Set

The Safety Set will consist of all patients who are enrolled in the study and either receive at least 1 dose of eteplirsen in the eteplirsen-treated group or have at least 1 post-Baseline safety assessment in the untreated control group.

For patients in the untreated control group, any safety assessment (including AE assessment) on or after the Week 1 visit, will be considered a post-Baseline safety assessment.

5.4. Muscle Biopsy Set

The muscle biopsy set will consist all patients who receive at least 1 dose of eteplirsen and have both baseline and 1 post-dose muscle biopsy sample evaluable for dystrophin expression.

5.5. Pharmacokinetic Set

The PK dataset will consist of all patients in the eteplirsen-treated group who receive a full dose of eteplirsen at the visits where PK sampling was done and for whom there are adequate PK samples from which to estimate population PK parameters.

6. GENERAL STATISTICAL METHODS AND CONVENTIONS

6.1. General Methods

Summary statistics will be presented by treatment group, unless stated otherwise.

For continuous variables, descriptive statistics will include the number of patients with data to be summarized (n), mean, SD, median, minimum, and maximum.

For categorical/qualitative variables, descriptive statistics will include frequency counts and percentages. The total number of patients in a treatment group will be used as the denominator for percentage calculations, unless stated otherwise.

For time-to-event data with censoring, the Kaplan-Meier (KM) method will be used to summarize the data.

[figure not shown]
6.2. Handling of Missing Data

6.2.1 Imputation of Missing Values

6WMT distance

If the patient is confirmed to have LOA (section 6.7), a value of 0 (zero) meters will be imputed for any missing values at the time or after the confirmation of LOA.

CCI

NSAA item and total score

If 4 or fewer of 17 NSAA items are missing, the score for the missing items will be assigned a value of zero. The NSAA total score will be calculated as the sum of the scores for the completed items. The total NSAA score will be treated as missing values when 5 or more items are missing.

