10.3.2.2. North Star Ambulatory Assessment (NSAA)

The NSAA will be performed for patients in both the treated and untreated control groups at the time points specified in Section 2. The NSAA is a clinician-administered scale that rates patient performance on various functional activities (Mazzone 2010). During this assessment, patients will be asked to perform 17 different functional activities, including a 10 meter walk/run, rising from a sit to stand, standing on one leg, climbing a box step, descending a box step, rising from lying to sitting, rising from the floor, lifting the head, standing on heels, and jumping. Patients will be graded as follows: 2 = normal, no obvious modification of activity; 1 = modified method but achieves goal independent of physical assistance from another; and 0 = unable to achieve goal independently. The NSAA will be performed on 2 consecutive days.

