13. STATISTICAL METHODS AND PLANNED ANALYSES

13.1. General Considerations

This section describes the rules, conventions, statistical analysis, and presentation of data for this study. Full details will be provided in the final Statistical Analysis Plan (SAP) for this study.

Revisions during the study may be made to accommodate protocol amendments and to make changes to adapt to unexpected issues in study execution that could affect planned analyses. Any revisions will be based on blinded review of the data. A formal SAP for the analysis and presentation of data from this study will be prepared and issued before database lock. The SAP will provide a more technical and detailed description of the proposed data analysis methods and procedures. Deviations from the statistical analyses outlined in this protocol will be included in this plan; any further modifications will be noted in the clinical study report (CSR). All statistical analyses will be performed by or under supervision of the Sponsor.

All available data will be included in data listings and tabulations. No imputation of values for missing data will be performed. Percentages of patients with AEs or laboratory abnormalities will be based on non-missing values.

[figure not shown]
All data collected in this study will be presented using summary tables and patient data listings. Summary statistics for raw and change from Baseline data of continuous variables will minimally include n, mean, standard deviation (SD), minimum, median, and maximum. For categorical variables, frequencies and percentages will be presented. Graphical displays will be provided as appropriate.

Endpoints will be assessed primarily using simple descriptive statistics and/or inferential statistics. Baseline will generally be defined for the treated group as the last available value before dosing, and the equivalent time point for the untreated control group.

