The duration of corticosteroid treatment, in months, will be calculated as (Day 1 – Date on which the patient started corticosteroid treatment + 1)/30.4375.

Corticosteroid Schedule

Corticosteroid schedules will include:

- Continuous (daily)
- Intermittent (includes all dosing schedules that do not require the patient to take at least one dose per day)

Non-Ambulatory Status and Loss of Ambulation (LOA)

The non-ambulatory status will be considered as “Yes” if all 3 conditions below are met:

- NSAA walk subscore as “0” (unable to achieve goal independently) on 2 consecutive days within a visit or NSAA was not done due to reason related to non-ambulation
- 6-minute walk test was not done with any reason related to permanent non-ambulation
- No later data showing this patient is still ambulatory. This is not required if non-ambulatory status occurs at the time of early withdrawal, or at the end of Week 96 assessment.

Note, when the NSAA or 6MWT is “Not Done” and the patient meets the non-ambulatory requirements above, a query will be issued to sites to confirm the permanence of non-ambulatory status. Prior to final database lock, the results of queries will be reviewed by Medical Director and Data Management and provided as documentation for non-ambulatory status determination.

Time to LOA is defined as the time from the initiation of eteplirsen for eteplirsen-treated patients, or Week 1 visit for untreated control patients to the first time of permanent non-ambulation. Patients who do not lose ambulation at the time of early withdrawal, or at the end of Week 96 assessment, whichever is earlier, the patient will be censored at the last time at which the patient is determined to be ambulatory.

NSAA and Total Score

The NSAA is a clinician-administered scale specifically designed for DMD patients that rates patient performance on various functional activities. Patients will be asked to perform 17 different functional activities including: stand, walk, stand up from chair, stand on one leg - right, stand on one leg - left, climb box step - right, climb box step - left, descend box step - right, descend box step - left, lift head, get to standing, rise from floor, stand on heels, jump, hop right leg, hop left leg, run 10 meters. Patients will be graded as follows

- 2 = achieves goal without any assistance;
- 1 = modified method but achieves goal independent of physical assistance from another person; and
- 0 = unable to achieve goal independently.

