7.8. Efficacy Analyses

For any efficacy assessment that is taken on 2 consecutive days within a visit (ie, 6MWT, NSAA items and total score, FVC % predicted), the average value will be used. If the assessment is taken or available only on 1 day, then the value on that day will be used. A value that is marked as invalid or not completed successfully on the eCRF will be considered a missing value.

Analyses of the primary and secondary efficacy endpoints will be performed separately on the primary efficacy set, the efficacy set, and the subset of patients with Baseline 6MWT distance >450 meters.

Due to the high dropout rate in the untreated group, comparisons between the eteplirsen-treated group and the untreated control group will not be meaningful. Therefore, only summaries by treatment group will be presented.

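### Missing NSAA items are scored as failures whatever the reason, and the SAP does not say whether the two test days are combined before the zero is applied

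*SAP*

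**What the plan says.** SAP 6.2.1 gives the rule for incomplete North Star Ambulatory Assessments: "If 4 or fewer of 17 NSAA items are missing, the score for the missing items will be assigned a value of zero". It adds "The NSAA total score will be calculated as the sum of the scores for the completed items", so there is no prorating, and then "The total NSAA score will be treated as missing values when 5 or more items are missing". None of these sentences depends on the reason the item is missing.

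The scoring key gives zero a specific meaning. Protocol 10.3.2.2 reads "0 = unable to achieve goal independently". The top score in SAP 6.7 is "2 = achieves goal without any assistance".

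The NSAA is performed on two consecutive days at each functional visit. SAP 7.8 opens its rule with "For any efficacy assessment that is taken on 2 consecutive days within a visit". It then calls for the average, names both the NSAA items and the total score, and falls back on the single day when only one is available. SAP 6.7 has the same rule for Baseline. SAP 7.8 also turns values flagged on the eCRF as invalid or unsuccessful into missing values.

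Protocol 13.1 says "No imputation of values for missing data will be performed". It also says that the SAP will include deviations from the protocol's analyses.

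**The concern.** An item that was not collected is not the same as an item that was failed. Under SAP 6.2.1 they enter the total identically, so a boy who could have done a skipped item is recorded as unable to do it.

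The SAP is more careful elsewhere. A missing 6MWT becomes zero metres only after confirmed loss of ambulation (SAP 6.2.1). A missing NSAA counts as loss of the ability to rise only when the reason relates to inability (SAP 6.7). The item rule has no such condition.

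The order of operations is also open. Two programmers could follow SAP 6.2.1 and 7.8 faithfully and produce different visit totals for the same boy.

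At stake is a named secondary endpoint, change from Baseline in NSAA total score, reported as means and plots by visit. The heading in SAP 6.2.1 covers item scores as well as the total. An imputed zero could therefore also reach the rise-from-floor and walk subscores that SAP 6.7 uses to define loss of those abilities.

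**Working it through.** **Inputs.** 17 items, each scored 0 to 2 (SAP 6.7). Up to 4 missing items are zero-filled, and 5 or more make the total missing (SAP 6.2.1). Two days are averaged, or the single available day is used (SAP 7.8).

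**1. The plan's own figure.** Maximum total = 17 × 2 = 34, as SAP 6.7 states.

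**2. Largest understatement of one day's total.** With m missing items, each of which the boy would have scored 2, the shortfall is 2m. For m = 1, 2, 3, 4 it is 2, 4, 6 and 8 points. The last is 8/34 = 23.5% of the scale.

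**3. Effect on the visit value.** Take a boy whose true total is 26 on both days. Day 1 is complete. The items missing on Day 2 include four that he would score 2 on.

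| Items missing on Day 2 | Order of operations | Day 2 total | Visit total |
|---|---|---|---|
| 4 | Zero-fill, then average day totals | 26 − 8 = 18 | (26 + 18)/2 = 22 |
| 5 | Day 2 total missing, Day 1 used alone | missing | 26 |
| 4 | Combine items across days, then sum | not needed | 26 |

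In the first order, losing a fifth item removes the error that losing four created. If the same four items are missing on both days, or only the incomplete day exists, the visit total is 18 and the full 8 points are lost. If he could not have done the four items, zero is correct and there is no error.

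**4. Change from Baseline.** The total itself can only be understated. The change is the later value minus Baseline, so zeros at Baseline create a false gain and zeros later create a false loss. The extremes are −8 and +8, or −4 and +4 if the items are missing on one of two averaged days.

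**5. Group mean, under assumptions.** The documents give no frequency of missing items. Suppose a share q of patients has m = 4 items missing on both days, with mean achievable score s on those items. The shift in the group mean at that visit is −q × m × s.

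- s = 1: q = 5% gives −0.05 × 4 × 1 = −0.2; q = 20% gives −0.8.
- s = 2: q = 5% gives −0.4; q = 20% gives −1.6.

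These values of q and s are illustrative only.

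**6. Is prorating clearly better?** From an observed 18 on 13 completed items, prorating gives 18 × 17/13 = 23.5. If the missing items would all have scored 2, the truth is 26, and prorating comes closer than 18. If he could not have done them, the truth is 18, and prorating overstates by 5.5. Neither rule is best in every case.

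**The case against.** The strongest reply is that SAP 7.8 may already contain the main repair. It lists NSAA items, not only the total, among the values averaged over two days, and it uses the single day when only one is available. Applied item by item, an item missing on one day takes the other day's value, and the 26-to-22 example disappears. This stands in part. A reader might infer that the SAP definitely averages a zero-filled day with a complete one, but the text does not say so. Listing items and total as separate averaged quantities makes that reading natural without making it the only one. The supportable defect is that the order is unstated.

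Three other strong readings also go beyond the documents.

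- **Eight points as a typical bias.** It is a ceiling for one boy at one visit. No missing-item rate is given, and nothing shows that missingness differs between visits or groups.
- **A distorted treatment test.** SAP 6.3, 7.8 and 8.1 rule out any test between the treated and untreated groups, and the NSAA total is summarised descriptively. SAP 4.4.2 defers the external-control evaluation to a supplemental SAP that is not among the documents. The rule would matter there only if that plan uses the NSAA total.
- **A breach of the protocol.** Protocol 13.1 allows the SAP to deviate if it says so. SAP 6.2.1 states its rule openly, and two entries in SAP 8.1 are blacked out, so nobody can say the change is unlisted. This is a point to reconcile.

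It is also fair to say that items may go unrecorded because a declining boy cannot do them, in which case zero is right. That argues for conditioning on the reason, which the rule does not do.

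**Conclusion.** The point holds as a defect of definition. SAP 6.2.1 scores a missing item as inability whatever the reason, and SAP 7.8 leaves open whether the days are combined before this is done.

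If day totals are zero-filled first, one incomplete day can lower a visit total by up to 4 points. The ceiling is 8 of 34, when four items that the boy would score 2 on are missing on both days or on the only available day. If items are combined first, the one-day error is nil. It is also nil wherever inability is the true reason. Change from Baseline can move either way.

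How often this would occur cannot be judged from the documents. Because the endpoint is descriptive in this SAP, the point is worth correcting but does not threaten any inference planned here.

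The risk to the subscores is narrower. For ambulation, SAP 6.7 also requires an undone 6MWT for a reason of permanent non-ambulation and no later evidence of walking, so an imputed walk zero cannot trigger loss by itself. The rise-from-floor definition has fewer safeguards: a zero on both days is enough for loss at that visit. Permanent loss then needs every later visit to agree.

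**What to change.** In SAP 6.2.1 and 7.8:

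1. Combine NSAA items across the two days of a visit first, using the other day's score when an item is missing on one day. Apply the same order at Baseline (SAP 6.7).
2. Assign zero only to items still missing where the recorded reason is inability, in line with the approach in SAP 6.7.
3. For items missing on both days for another reason, keep the existing five-item limit and report a sensitivity summary beside the zero-filled total, for example prorated or with the total set to missing. Showing both avoids relying on either assumption.
4. State that imputed zeros do not feed the rise-from-floor or walk subscores unless the reason is inability.
5. Reconcile the rule with the no-imputation sentence in protocol 13.1, and list it in SAP 8.1 if it is not already there.

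The cost is SAP wording and minor programming, using second-day data already collected. The main dependency is that the reason for a missing item is recorded. SAP 6.7 refers to reasons when the NSAA is not done or missing, but the documents do not show that a reason is captured for every item. Where it is not, step 3 applies.
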